10. Any history of non-infectious pneumonitis < 6 months prior to Screening.
11. Any active inflammatory bowel disease such as Crohn's disease or ulcerative colitis which are generally excluded or active autoimmune thyroiditis present < 6 months prior to Screening.
12. Type I diabetes.

13. History of CNS disease such as stroke, seizure, encephalitis, or multiple sclerosis (< 6 months prior to Screening).
14. Any history of motor neuron disorder or disease that affects motor neuron function.
15. Ongoing immune-related AEs (irAEs) and/or AEs \geq Grade 2 not resolved from previous therapies except vitiligo, stable peripheral sensory neuropathy up to Grade 2, hair loss, and stable endocrinopathies with substitutive hormone therapy.
16. Active allergy requiring systemic treatment (with the exception of histamine H1 receptor blocker treatment) or active infections requiring systemic anti-infectious therapy.
17. History of or clinical evidence of CNS primary tumors or metastases including leptomeningeal metastases, unless they have been previously treated, demonstrated no progression at least for 3 months before Screening, are asymptomatic and have had no requirement for steroids or enzyme inducing anticonvulsants in the last 14 days before Screening – subjects with suspected brain metastases at Screening should undergo a CT/MRI of the brain prior to study entry.
18. Systemic steroids at a daily dose of > 10 mg of prednisolone, > 2 mg of dexamethasone or equivalent, except non-systemic (inhaled, topical, nasal), for the last 28 days and ongoing.
19. Subjects with rapidly progressing disease (as per Investigator assessment), which may predispose to inability to tolerate treatment and/or study procedure.
20. Major surgery within last 4 weeks prior to Screening.
21. Known/expected hypersensitivity against CTL-002 and/or anti-PD-1/PD-L1 agents or their ingredients or previously had a severe hypersensitivity (\geq Grade 3) reaction to treatment with monoclonal antibodies (including pembrolizumab, nivolumab, cemiplimab etc.) and/or any of their excipients.
22. Evidence for active infection with human immunodeficiency virus (HIV), hepatitis B virus (HBV), hepatitis C virus (HCV), tuberculosis (TB), or severe acute respiratory syndrome coronavirus 2 (SARS-CoV-2) as per adequate testing performed.
23. Dementia or altered mental status that would prohibit informed consent.

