16. Active allergy requiring systemic treatment (with the exception of histamine H1 receptor blocker treatment) or active infections requiring systemic anti-infectious therapy.
17. History of or clinical evidence of CNS primary tumors or metastases including leptomeningeal metastases, unless they have been previously treated, demonstrated no progression at least for 3 months before Screening, are asymptomatic and have had no requirement for steroids or enzyme inducing anticonvulsants in the last 14 days before Screening – subjects with suspected brain metastases at Screening should undergo a CT/MRI of the brain prior to study entry.
18. Systemic steroids at a daily dose of > 10 mg of prednisolone, > 2 mg of dexamethasone or equivalent, except non-systemic (inhaled, topical, nasal), for the last 28 days and ongoing.
19. Subjects with rapidly progressing disease (as per Investigator assessment), which may predispose to inability to tolerate treatment and/or study procedure.
20. Major surgery within last 4 weeks prior to Screening.
21. Known/expected hypersensitivity against CTL-002 and/or anti-PD-1/PD-L1 agents or their ingredients or previously had a severe hypersensitivity (\geq Grade 3) reaction to treatment with monoclonal antibodies (including pembrolizumab, nivolumab, cemiplimab etc.) and/or any of their excipients.
22. Evidence for active infection with human immunodeficiency virus (HIV), hepatitis B virus (HBV), hepatitis C virus (HCV), tuberculosis (TB), or severe acute respiratory syndrome coronavirus 2 (SARS-CoV-2) as per adequate testing performed.
23. Dementia or altered mental status that would prohibit informed consent.
24. Any other diseases, metabolic dysfunction, physical examination finding, or clinical laboratory abnormality giving reasonable suspicion of a disease or condition that in the opinion of the Investigator would contraindicate the use of an investigational drug.
25. Receipt of any organ transplantation, including hematopoietic cell transplantation, but with the exception of transplants that do not require immunosuppression (e.g., corneal transplant, hair transplant).

26. Paraneoplastic syndrome (PNS) of autoimmune nature, requiring systemic treatment (systemic steroids or immunosuppressive agents) or a clinical symptomatology suggesting worsening of PNS.

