3.3. Discontinuation of Study Treatment and Subject Withdrawal Criteria

Subjects are at any time free to withdraw from the study, without prejudice to further treatment (withdrawal of consent). Such subjects will always be asked about the reason(s) and the presence of any AEs. If possible, they will be seen by an Investigator and undergo the End of Treatment Visit (see [Section 6.1.9](#)) and assessments and procedures scheduled for the follow-up (see [Section 6.1.11](#)). Adverse Events should be followed up (see [Section 7.2.1](#)). More detailed guidance on Dose Modification and Discontinuation criteria is given in [Section 5.3](#).

Subjects must be discontinued from the study in the following situations:

1. Occurrence of any AEs that are deemed to be clinically significant in the opinion of the Investigator and/or the SRC and warrant that a subject must discontinue treatment and be withdrawn from the study.
2. DLT in Part A (Phase 1; dose escalation).
3. Severe non-compliance to this protocol as judged by the Investigator and/or the SRC.
4. Confirmed disease progression.
5. Subjects incorrectly initiated on CTL-002 or the defined checkpoint inhibitor.
6. Use of prohibited concomitant drug, as defined in [Section 5.4.3](#).
7. Pregnancy.
8. Withdrawal of consent.
9. Participation in any other clinical trial.

3.4. Procedures for Handling Subjects Incorrectly Initiated on CTL-002 and/or the Defined Checkpoint Inhibitor

Subjects who fail to meet the inclusion/exclusion criteria should not, under any circumstances, be enrolled to receive study medication. There can be no exceptions to this rule.

Where subjects who do not meet the inclusion criteria and have been enrolled or started treatment with CTL-002 (or the defined checkpoint-inhibitor) in error, the Investigator shall inform the Medical Monitor and the SRC immediately. The Investigator will discuss with the SRC and the subject the best way forward and whether study treatment should be aborted or continued. The decision making has the intent to provide the subject with the best possible solution for his/her situation. The Investigator and Medical Monitor are to ensure that all such decision making is appropriately documented.

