5.1.1. Potential Organ Toxicity During CTL-002 Treatment

Investigators should monitor carefully for any potential organ disturbances under CTL-002 treatment based upon a potential excessive shift of immune cells into organs under stress.

Any signs of:

- Myocardial infarction or other hypoxic event of clinical significance
- Heart failure
- CNS hypoxic events
- Pneumonia, sepsis, any severe organ infection
- Liver failure of any type
- Kidney failure of any type
- Pancreatitis, pneumonitis, colitis, hepatitis, thyreoditis or any other "-itis" of clinical relevance
- Any other major hypoxic, toxic, metabolic or immunologic event with significant organ stress or damage

should result in an immediate careful evaluation of kinetics and degree of toxicity and a potential need for dosing interruption and/or medical intervention.

Immunosuppressive treatment may be required if excessive immune-cell infiltration of tissues (in line with mode-of-action of CTL-002) is at least suspected as possible causative factor for any such organ damage and if any such damage requires immediate intervention as per opinion of the Investigator.

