5.4.3. Prohibited Medications

The following are prohibited during the study:

- Chemotherapy, surgery or radiation therapy for cancer are not allowed during active participation with the exception of palliative intent. Likewise, use of any unapproved (i.e., no marketing authorization has been granted) IMP, other than CTL-002/the defined anti-PD-1 checkpoint inhibitor, or device is not allowed until a subject has completed the End of Core Study/Safety Follow-up Visit and enters the long-term Follow-up Period part of the study
- Corticosteroids and other immunosuppressive compounds are prohibited during active participation, except for:
 - a. Inhaled or topical steroids for short term use.
 - b. Prednisone or equivalent used to treat any condition other than immune-mediated AEs at a dose of ≤ 0.125 mg/kg/day of prednisone (maximum allowed 10 mg/day) for more than 7 consecutive days or at a dose of >0.125 mg/kg/day prednisone for less than 7 consecutive days.
 - c. Corticosteroids used to treat immune-mediated AEs.
 - d. Immunomodulating agents.
 - e. Anti-PD-1 checkpoint inhibitor determined as combination treatment product in this protocol.

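### Below 80 kg, exclusion 18 admits a steroid dose that section 5.4.3(b) goes on to prohibit, and section 3.3 then requires discontinuation

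*Protocol*

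**What the plan says.** At entry, exclusion 18 in protocol section 3.2 bars "Systemic steroids at a daily dose of > 10 mg of prednisolone, > 2 mg of dexamethasone or equivalent". It is qualified by "except non-systemic (inhaled, topical, nasal), for the last 28 days and ongoing", and the synopsis carries the same criterion. There is no weight term, so an ongoing 10 mg/day of prednisolone is admissible in any adult.

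On study, section 5.4.3 prohibits corticosteroids and other immunosuppressive compounds except for a list of items. Item (b), for conditions other than immune-mediated adverse events, has two limbs. The long-term limb allows prednisone or equivalent "at a dose of ≤ 0.125 mg/kg/day of prednisone (maximum allowed 10 mg/day) for more than 7 consecutive days". The short-course limb continues "or at a dose of >0.125 mg/kg/day prednisone for less than 7 consecutive days". Item (c) exempts "Corticosteroids used to treat immune-mediated AEs". Item (d) exempts immunomodulating agents without defining them.

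On consequences, section 3.3 opens its list with "Subjects must be discontinued from the study in the following situations", and item 6 reads "Use of prohibited concomitant drug, as defined in" section 5.4.3.

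**The concern.** Entry uses a flat limit and the on-study rule a weight-based one, with nothing leading from the first to the second. A subject can satisfy every eligibility criterion, keep taking the same dose, and come under a discontinuation rule that gives the investigator no discretion. The taper instructions in Table 4 and section 5.2.7.1 concern steroids started for immune-related events on study, not steroids the subject brings in. The permission in section 5.2 to modify supportive care without a deviation does not extend to sections 5.4.3 or 3.3.

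At stake is the needless withdrawal of a patient with non-curable disease, or a deviation that sites handle in different ways. The statistical analysis is not at stake.

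**Working it through.** **Inputs**
- Entry ceiling: 10 mg/day prednisolone, from exclusion 18 (section 3.2 and synopsis).
- Long-term on-study ceiling: the smaller of 0.125 mg/kg/day and 10 mg/day prednisone, from section 5.4.3(b).
- Above 0.125 mg/kg/day: fewer than 7 consecutive days only, same item.
- Assumption: prednisone and prednisolone count equally, mg for mg.

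**Weight at which the limits agree**

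10 mg/day ÷ 0.125 mg/kg/day = 80 kg.

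**Size of the gap below that weight**

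On-study limit = min(0.125 × weight, 10). Gap = 10 − limit. Reduction needed from 10 mg/day = gap ÷ 10.

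| Weight (kg) | On-study limit (mg/day) | Gap (mg/day) | Reduction needed |
|---|---|---|---|
| 50 | 0.125 × 50 = 6.25 | 3.75 | 37.5% |
| 60 | 0.125 × 60 = 7.5 | 2.5 | 25% |
| 70 | 0.125 × 70 = 8.75 | 1.25 | 12.5% |
| 80 | 0.125 × 80 = 10 | 0 | 0% |

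Above 80 kg the 10 mg cap binds and the gap stays at 0.

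**One subject followed through**

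Take a 60 kg subject on a stable 10 mg/day for a condition that is not an immune-mediated adverse event.
1. Exclusion 18: the dose is not above 10 mg/day, so the subject is eligible.
2. Section 5.4.3(b): 10/60 = 0.167 mg/kg/day, above 0.125, so only the short-course limb applies.
3. Counting from the start of active participation, that limb has run out by day 7, and the long-term limb does not allow the dose. It is now prohibited.
4. Section 3.3 item 6: discontinuation is required.

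The dose has not changed between steps 1 and 4.

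**Who is outside the problem**

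Anyone of 80 kg or more; anyone at or below 0.125 mg/kg/day; and anyone whose steroid treats an immune-mediated adverse event, since item (c) covers that without a dose cap.

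**The boundary at 7 days**

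One limb covers more than 7 days and the other fewer than 7, so a course of exactly 7 days above 0.125 mg/kg/day falls under neither.

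**The case against.** The strongest reply is that the two rules do different jobs. Exclusion 18 decides who may enter; section 5.4.3 decides what may be taken afterwards. A subject can satisfy both by staying at or below 0.125 mg/kg/day. A tighter on-study limit may well be deliberate, because section 5.2.2 warns that systemic steroids may weaken the study drug's effect. Section 5.4.1 tells sites to take section 5.4.3 into account. Section 5.4.2 has every medication at consent recorded with dose and reason, and sends questions to the Medical Monitor. This stands as an argument that many sites would notice in time. It does not remove the fault: no text tells an entrant to reduce the dose, and nothing cited allows section 3.3 item 6 to be waived.

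The reply is also right that the group is narrow. Exclusions 9, 17 and 26 remove many steroid users. Exclusion 15 admits stable endocrinopathies on hormone replacement. Where these follow earlier anti-PD-1/PD-L1 treatment, the replacement steroid can be read as falling under item (c), which is not limited to events arising on study.

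A reader might go further and infer that the protocol forbids the rescue immunosuppression it recommends, because item (c) names corticosteroids only. Section 5.1.1 says "Immunosuppressive treatment may be required if excessive immune-cell infiltration of tissues" is suspected, section 5.1.2 is similar, and section 5.2.7.1 asks sites to consider other immunosuppressants when corticosteroids fail. The documents do not support that inference. Immunosuppressive treatment includes corticosteroids, which item (c) exempts. Item (d) sits in a list of exceptions to a ban on immunosuppressive compounds, so it plausibly frees such agents, and section 5.2.7.1 expressly contemplates them. What remains is an undefined term. It matters mainly for events after which Table 4 lets dosing resume, such as Grade 2 colitis.

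**Conclusion.** The mismatch is real and follows from the text. For a subject under 80 kg on systemic steroids for something other than an immune-mediated adverse event, a dose above 0.125 mg/kg/day and up to 10 mg/day is acceptable at entry. Once continued for 7 or more consecutive days on study, it becomes a ground for mandatory discontinuation. The gap is 3.75, 2.5 and 1.25 mg/day at 50, 60 and 70 kg, and nil from 80 kg.

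This rests on counting prednisone and prednisolone as equal, and on reading section 3.3 item 6 as written. The protocol gives no figure for how many subjects enter on such doses; the number is likely small. It should not be read as covering every lighter subject on steroids, or as touching any efficacy or safety conclusion. The exactly-7-days gap is a drafting slip, and the rescue-treatment wording is an ambiguity. The point merits correction because, followed exactly, the rule withdraws a subject whom the eligibility criteria admitted on the same dose.

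**What to change.** Use one limit in both places. Which one is the sponsor's clinical decision.

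- **If the flat limit is acceptable:** set the long-term limb of section 5.4.3(b) to at most 10 mg/day prednisone or equivalent, and start the short-course limb above 10 mg/day. The gap is then 0 at every weight.
- **If the tighter limit is intended:** keep section 5.4.3(b) and write the same ceiling (0.125 mg/kg/day, maximum 10 mg/day, prednisone or equivalent) into exclusion 18, in section 3.2 and the synopsis. Exempt physiologic replacement therapy in both places.

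A blanket instruction to taper all entrants before Day 1 is not advised, since it would catch subjects on replacement therapy.

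Two minor wording changes can go with it: make the short-course limb cover no more than 7 consecutive days, and state in item (c) or (d) that non-steroid immunosuppressants given for immune-related events under section 5.2.7.1 are permitted.

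The cost is wording only, with no new data or procedures. Section 3.3 item 6 already points to section 5.4.3 and can stay. Because the change may affect a subject's treatment, section 9.3.1 requires prior ethics committee and competent authority approval, so it is best carried in the next amendment.

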5.5. Overdose

No data on overdosing with CTL-002 are available since this is the first study in humans. There is no known antidote.

For the purpose of this protocol, an overdose is defined as:

- Any subject receiving a higher dose of CTL-002 than the dose(s) assigned to a subject in any particular dosing cohort (applies to both Part A and B), or any subject administered a dose higher than 20 mg/kg of CTL-002
- Any subject receiving a dose of nivolumab higher than 240mg
- Any subject receiving a dose of cemiplimab higher than 350 mg

Investigators should be advised that any subject who receives a dose of CTL-002 and/or nivolumab/cemiplimab higher than that intended should be monitored closely, managed with appropriate supportive care and followed up expectantly. If the overdose results in an AE, the subject should be followed up carefully until all signs of toxicity are resolved.

For overdoses of nivolumab/cemiplimab refer to the leaflet insert.

For the purposes of the study such overdoses should be recorded as follows:

- An overdose with associated AEs/SAEs is recorded as the AE diagnosis/symptoms on the relevant AE modules in the eCRF, on the overdose eCRF module and reported using the SAE report form where applicable. This applies to situations where an AE is associated with (“results from”) the overdose of CTL-002 and/or nivolumab/cemiplimab, the AE(s) is reported as an SAE, even if no other seriousness criteria are met

- An overdose with no associated symptoms is only reported on the overdose eCRF module

If an overdose occurs in the course of the study, then Investigators or other site personnel must inform appropriate Sponsor representatives immediately, but **no later than 24 hours** of when he or she becomes aware of it.

For overdoses associated with an SAE, standard reporting timelines apply.

5.6. Treatment Compliance

The Investigator is responsible for maintaining accurate subject records to fully document the study drugs have been administered with details of dosing information.

CTL-002 and nivolumab/cemiplimab should only be used as directed in this protocol and as detailed in the Pharmacy Manual. Details of treatment with CTL-002 and nivolumab/cemiplimab for each subject will be recorded in the eCRF.

5.7. Randomization and Blinding

This is an open-label, single-arm study without randomization or blinding of data.

6. TRIAL PROCEDURES AND ASSESSMENT

6.1. Study Visits

During the study all subjects will undergo regular assessments (see below for further details). Adherence to the study design requirements, including those specified in the SoA, is essential and required for study conduct.

- Complete SoAs and their timing are provided in the SoAs see [Table 5](#), [Table 6](#) and [Table 7](#). More detailed description of laboratory procedures and sample management is provided in the Laboratory Manual.
- Descriptions of the different Efficacy and Safety Assessments are provided in [Section 6.2.5](#) and [Section 6.2.4](#), respectively
- Note the following guidance regarding visit windows, as far as not otherwise indicated in the SoA

6.1.1. Pre-screening Visit Part A (Phase 1; dose escalation)

Time point: Pre-screening assessment to confirm subject's GDF-15 serum levels.

This result should be available before a subject is approved for consent and starts screening procedures.

- Pre-screening informed consent (for collection of historical serum GDF-15 results within 2 months prior to the start of treatment with CTL-002 or in case of pre-screening blood sampling)
- Serum analysis of GDF-15. **Note:** Serum GDF-15 levels can be measured locally (if site routinely performs this assessment) or centrally.

The analysis of GDF-15 does not need to be repeated if there are historical serum GDF-15 results available within 2 months prior to the start of treatment with CTL-002

6.1.2. Screening Visit Part A (Phase 1; dose escalation) / Part B (Phase 2a; expansion)

Time point: Screening assessments (i.e., inclusion/exclusion criteria) to confirm subject eligibility will be performed within up to 21 days (Day -21 to Day -1) (for Part A) and up to 28 days (Day -28 to Day -1) (for Part B) prior to first dose.

All results should be available before a subject is declared eligible for study participation.

- Subject informed consent
- Medical history/current medical conditions, prior cancer therapies including radiation and surgery
- Demographics
- Eligibility criteria
- Vital signs
- SARS-CoV-2 (COVID-19) testing (RNA and antibody testing)
- Pregnancy test (women of childbearing potential only. Serum test for pregnancy within 7 days prior to Day 1 dose)

- Safety laboratory testing (hematology, clinical chemistry, coagulation)
- Safety urinalysis
- Assessment of thyroid hormones, hemoglobin A1c (HbA1c) and NT-proBNP (N-terminal B-type natriuretic peptide)
- Infectious disease/serology
- Immunoglobulins
- Immune monitoring (cytokines/chemokines) (Part A only)
- Serum analysis of GDF-15
- Urine analysis of GDF-15 (Part A only)
- Full physical examination (including height and weight) plus collection of historical weight data from ≤ 6 months prior Screening, as available
- ECOG Performance Status
- Neurological examination/assessment (check for motor neuropathy)
- ECG
- Echocardiography or MUGA if ECHO cannot be performed (MUGA/ECHO standard of care results can be used as long as assessed within screening period)
- Cutaneous tumor lesion assessment/photography
- Tumor assessment/Imaging: CT/MRI/positron emission tomography (PET)-Scan to document tumor burden according to RECIST/iRECIST (Refer to [Appendix 2](#)) (scans performed as standard of care can be used as long as made within screening period)
- L3SMI (Part A only)
- Mini Cachexia Score (MCASCO) (Part A only)
- X-ray thorax (only if CT/MRI/PET CT imaging older than 7 days)
- Mandatory tumor biopsy:
 - For Part A (Phase 1) to be taken between day -7 and Day -1
 - For Part B (Phase 2a) baseline biopsy from all subjects (new or archived if obtained within 120 days prior to treatment start), for melanoma and cutaneous squamous cell carcinoma ideally within -7 days before infusion of CTL-002

Note: for cutaneous squamous-cell carcinoma, multiple punch biopsies to be taken at a single timepoint (as per clinical possibility, ideally 3-5).
- Tumor mutational status:
 - For all subjects: collection of historical data e.g., but not limited to BRAF, CEA, PSA, CA19-9, CA-125, MSI, PD-L1, EGFR, Alk, HER2 and other molecular hallmark changes depending upon subject's primary cancer.
 - For subjects enrolled under this version of the protocol and under previous protocols v4.0 and 5.0, an optional retrospective analysis of PD-L1 and other relevant biomarkers might be conducted on archival tumor tissue any time after screening.

6.1.3. Part A (Phase 1; dose escalation): DLT Observation Period (Cycles 1 and 2)

Time-point: After confirmation of all study eligibility criteria – Weeks 1-4 (Cycles 1 and 2)

Note: On the day of study drug dosing, all procedures are to be performed pre-dose. Before start of first CTL-002 infusion, safety laboratory parameters will be assessed to reconfirm eligibility and ability to receive study treatment.

Cycle 1

Week 1: Day 1

- Medical history/current medical conditions, prior cancer therapies including radiation and surgery
- AEs
- Concomitant medications
- Physical examination
- ECOG
- ECG
- Safety laboratory testing (hematology, clinical chemistry, coagulation): Pre-CTL-002 infusion (within 24 hours prior to dosing to reconfirm eligibility criteria) and 6 hours after the start of CTL-002 infusion.
- Safety urinalysis
- Urine pregnancy test (if positive, to be confirmed with serum test)
- Urine analysis of GDF-15 (prior to infusion)
- Immune monitoring (cytokines/chemokines): Sample taken within 30 minutes prior to CTL-002 infusion
- PK: Sample taken within 30 minutes prior to CTL-002 infusion, then immediately before the end of CTL-002 infusion (1 hour) and 4 hours (± 15 minutes), and 8 hours (± 30 minutes) after the start of CTL-002 infusion.
- Serum analysis of GDF-15: Sample taken within 30 minutes prior to CTL-002 infusion, then immediately before the end of CTL-002 infusion (1 hour) and 4 hours (± 15 minutes) and 8 hours (± 30 minutes) after the start of CTL-002 infusion.
- Immunogenicity/ADA testing: Sample taken within 30 minutes CTL-002 prior to infusion
- Blood molecular/transcriptional profiling: Sample taken within 30 min prior to CTL-002 infusion
- Vital Signs (immediately before CTL-002 infusion and then 15 min (± 5 min), 30 min (± 5 min), 60 min (± 15 min), 90 min (± 15 min), 2 hrs (± 15 min), 4 hrs (± 15 min) and 8 hrs (± 30 min) after the start of CTL-002 infusion)
- CTL-002 infusion over approximately 60 minutes (± 10 min) (**Note:** for “backfill” subjects, combination treatment is started immediately on Day 1, no prior monotherapy cycle)
- Overnight hospitalization/observation

Week 1: Day 2

- Vital signs
- AEs
- Concomitant medications
- Safety laboratory testing (hematology, clinical chemistry, coagulation)
- Safety urine analysis

- Urine analysis of GDF-15
- Immune monitoring (cytokines/chemokines): Sample taken 24 hours post-CTL-002 infusion (± 2 hours)
- PK: Sample taken at 24-hour time-point (± 2 hours)
- Serum analysis of GDF-15: Sample taken 24 hours post -CTL--002 infusion (± 2 hours)
- Blood molecular/transcriptional profiling: Sample taken 24 hours post-CTL-002 infusion (± 2 hours)

Week 2: Day 8 (± 24 hours)

- Vital signs
- AEs
- Concomitant medications
- Physical examination
- ECOG
- Safety laboratory testing (hematology, clinical chemistry, coagulation).
- Safety urinalysis
- Urine analysis of GDF-15
- Immune monitoring (cytokines/chemokines): Sample taken at Day 8 (± 24 hours)
- PK: Sample taken at Day 8 (± 24 hours)
- Serum analysis of GDF-15: Sample taken at Day 8 (± 24 hours)

Cycle 2

Week 3: Day 15 (± 2 days)

Note: On the day of dosing, all procedures to be performed pre-dose.

- AEs
- Concomitant medications
- Mandatory biopsy - To be taken within 48 hours prior to CTL-002 infusion (Day 15 biopsy not required for Dose level 3-5 “backfill” subjects)
- Physical examination
- ECOG
- Weight assessment
- ECG
- Safety laboratory testing (hematology, clinical chemistry, coagulation) – Pre-CTL-002 infusion (within 24 hours of dosing) and 6 hours after the start of CTL-002 infusion
- Assessment of thyroid hormones, HbA1c and NT-proBNP
- Safety urine analysis
- Urine pregnancy test (if positive, to be confirmed with serum test)
- Urine analysis of GDF-15
- Immune monitoring (cytokines/chemokines): Sample taken within 30 minutes prior to CTL-002 infusion
- PK: Sample taken within 30 minutes prior to CTL-002 infusion and immediately before end of CTL-002 infusion (1 hour)

- Serum analysis of GDF-15: Sample taken within 30 minutes prior to CTL-002 infusion and immediately before end of CTL-002 infusion (1 hour)
- Immunogenicity: Sample taken within 30 minutes prior to CTL-002 infusion
- Blood molecular/transcriptional profiling: Sample taken within 30 minutes prior to CTL-002 infusion
- Vital signs (immediately before CTL-002 infusion and 15 min (\pm 5 min), 60 min (\pm 15 min), 2 hrs (\pm 15 min) and 4 hrs (\pm 15 min) after the start of CTL-002 infusion)
- CTL-002 infusion over approximately 60 minutes (\pm 10 min) - 30 minutes before nivolumab infusion
- Nivolumab infusion over approximately 30 minutes (\pm 5 min)
- Overnight hospitalization/observation

Week 4: Day 22 (\pm 2 days)

- Vital signs
- AEs
- Concomitant medications
- Physical examination
- ECOG
- Safety laboratory testing (hematology, clinical chemistry, coagulation)
- Safety urine analysis
- Urine analysis of GDF-15
- Immune monitoring (cytokines/chemokines)
- PK
- Serum analysis of GDF-15
- MCASCO

